1 INTRODUCTION

The investigational medicinal product (IMP) tested in this trial is Sym013, referenced as Pan-HER. Pan-HER is a recombinant antibody mixture containing 6 humanized immunoglobulin G1 (IgG1) mAbs, which bind specifically to non-overlapping epitopes on the EGFR (Hu1277 and Hu1565), HER2 (Hu4384 and Hu4517) and HER3 (Hu5038 and Hu5082).

This is the first clinical trial to study Pan-HER.

HER family expression heterogeneity and plasticity in response to therapeutic intervention are important drivers of primary and acquired drug resistance and pose challenges to effective cancer treatment in the clinic. By targeting three receptors of the HER family, Pan-HER effectively inhibits a range of cancers of various tissue origin and genetic background, including cell lines and xenograft models with acquired resistance to therapeutic antibodies. Importantly, by down modulating all three targets simultaneously, Pan-HER prevents compensatory receptor up-regulation and renders the receptors unavailable for ligand binding and activation. Pan-HER represents a novel strategy to deal with primary and acquired resistance and thus may provide a clinically relevant effect in patient populations for which few therapeutic options exist.

Pan-HER is developed for the treatment of patients with resistant or refractory epithelial malignancies. Initially, the safety and efficacy of Pan-HER are investigated in advanced epithelial malignancies. Future development of Pan-HER may include pancreatic, esophageal, gastric, CRC, NSCLC, advanced ovarian, and HER2-positive breast cancer having failed HER2 targeted therapy.

The Statistical Analysis Plan (SAP) details the statistical methodology to be used in analyzing study data and outlines the statistical programming specifications, tables, figures, and listings. It describes the variables and populations, anticipated data transformations and manipulations, and other details of the analyses not provided in the clinical study protocol. This SAP covers the planned analysis of all data collected on paper (source documents /case report forms [CRFs]), captured electronically in DataLabs®, and provided by external vendors. PK/PD and immunogenicity blood samples are analyzed by external laboratory Eurofins Pharma. Tissue samples are analyzed by external laboratory Histogenex. Biomarkers blood samples are analyzed by external laboratory Guardant Health.

PAREXEL International
Statistical Analysis Plan Template for Early Phase Studies

Symphegen A/S

Sym013-01

The analyses described are based on Clinical Study Protocol (CSP) Final 7.0 incorporating Amendment No.6, dated 14/Jun/2018, Amendment No. 5, dated 23/Jan/2018, Amendment No. 4, dated 04/May/2017, Amendment No. 3, dated 26/Apr/2017, Amendment No. 2, dated 14/Nov/2016, Amendment No. 1, dated 03/Oct/2016 and original CSP Version Final 1.0, dated 13/Jun/2016. The analyses described are based upon electronic Case Report Form (eCRF), version 10.0 dated 18/Oct/2018.

The SAP will be finalized prior to database lock and describes the statistical analysis as it is foreseen when the study is being planned. If circumstances should arise during the study rendering this analysis inappropriate, or if in the meantime improved methods of analysis should come to light, different analyses may be performed. If this occurs, Symphegen will determine how the revision impacts the study and how the SAP revision should be implemented. The details of the revision will be documented and described in the clinical study report (CSR).

The study was designed to include a Part 1 (Dose-Escalation) followed by a Part 2 (Dose-Expansion).

During Part 1, Symphegen decided to stop the SYM013-01 enrollment. Therefore, no patient is enrolled in Part 2.

All protocol objectives planned data collection and analyses for Part 2 of the study will be omitted hereafter in this SAP.

PAREXEL International
Statistical Analysis Plan Template for Early Phase Studies

Symphogen A/S

Sym013-01

2 STUDY OBJECTIVES

2.1 Objectives of Part 1, Dose-Escalation

2.1.1 Primary Objective (Part 1)

To assess the safety and tolerability of Pan-HER when administered either Q1W or Q2W by IV infusion to separate dose-escalation cohorts of patients with advanced epithelial malignancies without available therapeutic options.

2.1.2 Secondary Objectives (Part 1)

1. To determine a recommended phase 2 dose (RP2D) and regimen of Pan-HER
2. To evaluate the pharmacokinetic (PK) profile of Pan-HER
3. To evaluate the immunogenicity of Pan-HER
4. To evaluate target engagement in skin biopsy tissue (EGFR and HER3) and tumor biopsy tissue, if available, (EGFR, HER2 and HER3)
5. To evaluate other potential pharmacodynamic biomarkers of Pan-HER action, and estimate, if feasible, the magnitude of biological activity in peripheral blood and in skin biopsy (and tumor biopsy, if available) tissue
6. To make a preliminary evaluation of the antitumor effect of Pan-HER

3 INVESTIGATIONAL PLAN

3.1 Overall Study Design and Plan

This is an open-label, multicenter trial composed of 2 parts in which Pan-HER will be evaluated when administered by the IV route to patients with advanced epithelial malignancies without available therapeutic options:

- Part 1 is a Phase 1a dose-escalation evaluating Q1W and Q2W schedules of administration in separate dose-escalation cohorts to determine the RP2D and regimen of Pan-HER.

PAREXEL International
Statistical Analysis Plan Template for Early Phase Studies

Symphogen A/S
Sym013-01

- During Part 1, cohorts of patients will receive increasing doses of Pan-HER on either Q1W or a Q2W schedule until establishment of the following for each schedule:
 - A maximum administered dose (MAD), the highest dose level administered (in mg/kg).
 - A maximum tolerated dose (MTD), the highest dose of SYM013 with <33% patients who have experienced dose limiting toxicity (DLT) as defined by the protocol during cycle 1 of study treatment. Q1W and Q2W regimens may have different MTDs;
 - A RP2D, determined based safety of Q1W and Q2W dose regimens as well as available PK and target engagement results, was to be identified. The RP2D may be equal to or lower than the MTD for the Q1W and/or Q2W dosing regimens.

The Part 1 starting dose of Pan-HER will be 1.0 mg/kg Q1W. The following dose levels of Pan-HER are planned to be evaluated:

Q1W

- Dose Level 1: 1 mg/kg Q1W
- Dose Level 2: 2 mg/kg Q1W
- Dose Level 3: 4 mg/kg Q1W
- *Dose Level 4P: 6 mg/kg Q1W + P (lower doses with prophylaxis may be explored, if indicated)
- *Dose Level 5P: 9 mg/kg Q1W + P
- *Dose Level 6P: 12 mg/kg Q1W + P (no patient enrolled in this dose level)
- *Dose Level 7P: 15 mg/kg Q1W + P (no patient enrolled in this dose level)
- *Dose Level 8P: 18 mg/kg Q1W + P (highest potential dose allowed per protocol) (no patient enrolled in this dose level)

PAREXEL International
Statistical Analysis Plan Template for Early Phase Studies

Symphogen A/S

Sym013-01

Q2W

- Dose Level 4: 6 mg/kg Q2W
- Dose Level 5: 9 mg/kg Q2W
- *Dose Level 5P: 9 mg/kg Q2W+ P
- *Dose Level 6P: 12 mg/kg Q2W+ P
- *Dose Level 7P: 15 mg/kg Q2W + P
- *Dose Level 8P: 18 mg/kg Q2W + P (highest potential dose allowed per protocol) (no patient enrolled in this dose level)

*Mandatory intensive IRR and oropharyngeal mucositis prophylaxis; 4-hour infusion (designated “P”)

Note: Patients entered to Dose Levels 1, 2 and 3 were treated Q1W. As of Amendment 3, the dosing schedule in this trial was changed to Q2W. Patients entered to the trial prior to implementation of this amendment could continue to be treated Q1W.

Note: As of Amendment 5, patients entered to Dose Level 5P and all patients thereafter must receive intensive prophylaxis on a mandatory basis to reduce the risk of IRRs and oropharyngeal mucositis, and must receive Pan- HER over a fixed (at minimum) 4-hour (+10 min) period unless further prolongation is required for an individual patient due to the occurrence of an IRR. For patients entered to the trial prior to Amendment 5, these changes could be implemented at the Investigator’s discretion based on the individual patient’s prior experience with Pan-HER dosing.

Note: As of Amendment 6, Q1W dosing is reintroduced under the prophylaxis and infusion duration conditions outlined in Amendment 5. All patients must receive intensive prophylaxis, as defined herein, on a mandatory basis to reduce the risk of IRRs and oropharyngeal mucositis, and must receive Pan-HER infusions over a fixed (at minimum) 4-hour (+10 min) period, unless further prolongation is required for an individual patient due to the occurrence of an IRR. Reevaluation of Q1W dosing will begin at the 6 mg/kg dose; however, lower doses may be explored if indicated based on tolerability.

Initially, one patient will be treated at each dose level until the occurrence of a toxicity during Cycle 1 that activates the stopping rule of the single-patient cohort titration design. If such a toxicity has not occurred in the first 3 cohorts (i.e., cohorts of 1 mg/kg, 2 mg/kg, and 4 mg/kg

PAREXEL International
Statistical Analysis Plan Template for Early Phase Studies

Sympogen A/S

Sym013-01

Q1W), the next cohort to open will be a 3-patient cohort and the design will switch to the 3+3 design.

Further dose-escalation will follow a standard 3+3 design with a target toxicity level of < 33% as determined by the number of cycle 1 DLTs.

During Part 1, intermediate dose level(s) between 2 planned dose levels may be evaluated to further characterize safety and tolerability of Pan-HER, if indicated based on toxicity observations and/or results from PK and/or target engagement analyses.

A safety monitoring committee (SMC) will be established and will include Investigator(s), Medical Monitor(s) and Sponsor's medical representatives. The SMC will review clinical and laboratory safety data regularly throughout the trial and will select the RP2D and regimen to be used in Part 2 based on safety data, as well as available PK and target engagement results.

[figure not shown]
The trial design is shown in Figure 1.

The overall Trial Plan is reported in Table - Overall Trial Plan.

PAREXEL International
Statistical Analysis Plan Template for Early Phase Studies

Symphogen A/S
Sym013-01

Figure 1 Overall Trial Design

Abbreviations: DLT: dose-limiting toxicity; G2T: grade 2 toxicity; MAD: maximum administered dose; MTD: maximum tolerated dose; P(): prophylaxis; RP2D: recommended phase 2 dose; Q1W: every week; Q2W: every second week.*

PAREXEL International
Statistical Analysis Plan Template for Early Phase Studies

Symphegen A/S
 Sym013-01

Table - Overall Trial Plan

Screening Period	
Screening	14 days within first dose of Pan-HER
Treatment Period	
Treatment Allocation	The allocated dose and schedule of Pan-HER will depend upon cohort assignment and will be confirmed by Sponsor or designee on the Screening and Allocation Form .
Pan-HER	
Pan-HER will be initiated on C1/D1 and based on cohort assignment, will be administered either Q1W or Q2W to separate dose-escalation cohorts of patients by IV infusion in cycles of treatment:
 
 • Q1W: Dosing on Day 1, 8, 15, and 22 of each 28-day cycle (± 2 days) • Q2W: Dosing on Day 1 and 15 of each 28-day cycle (± 2 days) 
The duration of infusion will be (effective with Amendment 5):
 
 • Minimum of 4 hours (+10 min) for all infusions. Titrated rate increases during infusions, and infusion duration reductions after C1/D1, will no longer be allowed. For Part 1 of the trial, Pan-HER will be administered following delivery of intensive prophylaxis, as defined herein, on a mandatory basis to reduce the risk of IRRs and oropharyngeal mucositis.
Discontinuation of Pan-HER	Treatment will continue until unacceptable toxicity or other conditions preventing further treatment, PD, termination of the trial, or patient's decision to withdraw.
End of Treatment	
End of Treatment Visit	Within 10 days after the decision to discontinue Pan-HER, an EOT Visit should be performed.

PAREXEL International
Statistical Analysis Plan Template for Early Phase Studies

Symphegen A/S
Sym013-01

Follow-up	
One Month Follow-up Visit	Follow-up continues until 1 month (30+7 days) after the last dose of Pan-HER. At that time, a 1M FUP Visit should be performed. This visit constitutes the end of trial participation for the patient.

Abbreviations (in alphabetical order): C1/D1, Cycle1/Day1; CR, complete response; EOT, End of Treatment Visit; IRR, infusion related reaction; IV, intravenous; 1M FUP, 1-Month Follow-up Visit; OS, overall survival; PD, progressive disease; PR, partial response; SD, stable disease.

3.2 Endpoints and Associated Variables

Refer to the Schedule of Assessments for timing of assessments.

Primary Endpoint - Part 1, Dose-Escalation

The primary objective of the dose-escalation part is to assess the safety and tolerability of Pan-HER. This will be assessed by the primary endpoint for Part 1: **occurrence of DLTs during Cycle 1 for each of the Pan-HER dose regimens.**

Secondary Efficacy Endpoints

- Documented OR, defined as documented PR or CR, from baseline to end of trial participation (in patients with measurable disease only) (as measured in Part 1)
- Best overall response by RECIST v1.1, categorized as Complete Response (CR), Partial Response (PR), Stable Disease (SD), Progressive Disease (PD), and Not Evaluable (NE)
- Disease Control Rate (DCR)
- Changes in sum of diameters of target lesions from baseline to end of trial participation
- Time to documented PD (Time To Progression [TTP])

PAREXEL International
Statistical Analysis Plan Template for Early Phase Studies

Symphogen A/S

Sym013-01

Secondary Safety Endpoints

- Nature, incidence and severity of AEs measured from baseline to end of trial participation
- AEs leading to dose-reductions, dose delays and permanent treatment cessation
- Changes in safety laboratory values from baseline to end of trial participation
- Changes in vital signs and physical examinations from baseline to end of trial participation
- Occurrence of ADA to Pan-HER measured in serum at selected timepoints from baseline to end of trial participation

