10.4.1 Efficacy Endpoints and Analyses

All statistical analysis of the secondary endpoints will be presented using the FAS.

The following anti-tumor response endpoints will be measured in Part 1:

• Documented OR, defined as documented PR or CR, from baseline to end of trial participation (in patients with measurable disease only)

The following anti-tumor response endpoints will be measured in Part 2:

- Changes in sum of diameters of target lesions from baseline to end of trial participation
- SD for >16 weeks from baseline
- Time to documented PD, death, patient withdrawal or end of trial participation, whichever comes first
- Overall survival (OS)

Best overall response by RECIST v1.1 will be summarized by trial part and cohort by means of counts and percentages for the categories CR, PR, SD, PD, and NE.

Number and percentages of patients with documented OR in the dose-escalation part will be presented including corresponding 95% exact Clopper-Pearson CI. All documented ORs (Part 1 and Part 2) will be listed including duration (in days) of OR, measured from time of first PR or CR to PD.

Duration of SD is calculated from baseline until first measurement of PD. The number and percentages of patients with SD for more than 16 weeks will be presented by trial part and tumor type.

Time to documented PD, death, patient withdrawal or end of trial participation, whichever comes first, will be presented in a Kaplan-Meier plot. The median progression free survival time, including 95% CI, will be derived. There will be one plot for Part 1, and plots for each of the 4 tumor types in Part 2.

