PR	NE	SD provided minimum criteria for SD duration met, otherwise NE
NE	NE	NE

CR = complete response, PR = partial response, SD = stable disease, PD = progressive disease, and NE = inevaluable.

a If a CR is truly met at first time point, then any disease seen at a subsequent time point, even disease meeting PR criteria relative to baseline, makes the disease PD at that point (since disease must have reappeared after CR). Best response would depend on whether minimum duration for SD was met. However, sometimes 'CR' may be claimed when subsequent scans suggest small lesions were likely still present and in fact the patient had PR, not CR at the first time point. Under these circumstances, the original CR should be changed to PR and the best response is PR.

Patients with non-target disease only, may have a time point response of NON-CR/NON-PD, these responses will be included in the count of SD.

Determinations of Best Overall Responses derived as described will be reviewed by Symphogen and PAREXEL on a patient by patient basis across time.

- Unconfirmed BOR by RECIST v1.1:

Per RECIST 1.1 [1]: in cases where confirmation of complete or partial response is not required the Best response is defined as the best response across all time points (for example, a patient who has SD at first assessment, PR at second assessment, and PD on last assessment has a best overall response of PR). When SD is believed to be best unconfirmed response, it must also meet the protocol specified minimum time from baseline.

PAREXEL International
Statistical Analysis Plan Template for Early Phase Studies

Symphegen A/S
Sym013-01

Patients with non-target disease only, may have a time point response of NON-CR/NON-PD, these responses will be included in the count of SD.

- Documented objective response (OR) confirmed and unconfirmed, based on determination of confirmed and unconfirmed best overall response (BOR) per RECIST v1.1.

Confirmed OR is defined as the percentage of patients who had confirmed CR or PR.

Unconfirmed OR is defined as the percentage of patients who had unconfirmed CR or PR.

'The duration of overall response is measured from the time measurement criteria are first met for CR/PR (whichever is first recorded) until the first date that recurrent or progressive disease is objectively documented (taking as reference for progressive disease the smallest measurements recorded on study). ' [1].

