4.5 Analysis Sets

Two analysis sets will be defined in accordance with the consolidated ICH E9 GCP guidelines.

The Full Analysis Set (FAS) will comprise all enrolled patients who have received at least one dose of Pan-HER. The FAS will be used for evaluation of all endpoints except evaluation of DLTs. The patients in the FAS will contribute to the analyses as allocated to treatment (patients will be reported below the regimen and dosage actually received). For the evaluation of PK endpoints, patients, full profiles, or single measurements can be excluded from the analyses with justification. The decision of excluding patients, full profiles, or part of profiles will be described in the clinical trial report (CTR).

The DLT Analysis Set will comprise all patients in the FAS enrolled in Part 1, except patients who did not complete Cycle 1 for reasons other than drug toxicity. The DLT Analysis Set will be used for evaluation of DLTs and the MTD or lack thereof.

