4.10.2 Analysis of Efficacy Variable(s)

All statistical analysis of the efficacy endpoints will be presented using the FAS.

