4.10.2.1 Anti-Tumor Response according to RECIST v1.1

The following anti-tumor response endpoints will be measured in Part 1:

- Confirmed and unconfirmed BOR by RECIST v1.1 will be listed and summarized by dose regimen and dose level received using frequency distribution for the categories CR, PR, SD, PD, and Not Evaluable.
- Number and percentage of patients with documented confirmed and unconfirmed OR will be summarized by dose regimen and dose level using frequency distribution with the corresponding 95% exact Clopper-Pearson Confidence Intervals (CI) for binomial proportion. All documented ORs will be listed including duration (weeks) of response.
- Patients in DCR will be listed and summarized by dose regimen and dose level using frequency distribution with the corresponding 95% exact Clopper-Pearson Confidence Intervals (CI) for binomial proportion.
- Time to Progression (TTP)

PAREXEL International
Statistical Analysis Plan Template for Early Phase Studies

Symphogen A/S
Sym013-01

The median TTP, as well as 26 weeks and 52 weeks TTP rates and the corresponding 95% CIs will be estimated using the product-limit method and presented using a Kaplan-Meier plot. Number and percent of censored patients will be presented, also number and percent of patients censored for death will be presented.

- Changes in sum of diameters of target lesions from baseline to end of trial participation
Changes in the sum of diameters of target lesions from baseline to end of trial participation will be listed as percentage and absolute value, the best change (i.e., largest reduction or smallest increase) will be identified and presented using summary table and plotted with a waterfall plot. Change in sum of diameters will also be presented by primary tumor type.
- Results of the tumor evaluation by CT/MRI for target lesions, non-target lesions and timepoint tumor response will be listed, as well as derived target and non-target time point responses.

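### Part 1 objective response is defined for patients with measurable disease only, but the SAP's derivation, analysis rule and output table use the FAS without that restriction, so the reported rate and exact CI need not match the defined endpoint.

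*SAP*

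**What the plan says.** **Endpoint.** Protocol 10.4.1 gives the Part 1 anti-tumor endpoint as "Documented OR, defined as documented PR or CR, from baseline to end of trial participation (in patients with measurable disease only"). SAP 3.2 repeats the restriction: "in patients with measurable disease only) (as measured in Part 1").

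**Analysis set.** Protocol 10.4.1 also says "All statistical analysis of the secondary endpoints will be presented using the FAS". SAP 4.10.2 says "All statistical analysis of the efficacy endpoints will be presented using the FAS". SAP 4.5 states: "The Full Analysis Set (FAS) will comprise all enrolled patients who have received at least one dose of Pan-HER". The only other analysis set is the DLT Analysis Set. No measurable-disease or response-evaluable set is defined.

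**Derivation and summary.** SAP 3.2.1.1 says "Confirmed OR is defined as the percentage of patients who had confirmed CR or PR", with a parallel sentence for unconfirmed OR. SAP 4.10.2.1 says "Number and percentage of patients with documented confirmed and unconfirmed OR will be summarized by dose regimen and dose level using frequency distribution", with exact 95% Clopper-Pearson intervals. Table 14.2.4.1, which combines best overall response (BOR), OR and disease control rate, is labelled Full Analysis Set and is starred for the abbreviated CSR.

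**Who can be in Part 1.** In Protocol 6.1, measurable disease is part of inclusion criterion 8, which applies to Part 2 only. SAP 3.2.1.1 provides a separate response table (its Table 2) for patients with non-target disease only, and counts their Non-CR/Non-PD responses as SD in BOR.

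**The concern.** The endpoint names one population and the instructions a programmer would follow name another. A PR needs a 30% fall in the sum of target-lesion diameters, so a patient without target lesions cannot have one. If such patients stay in the denominator, the percentage and its interval are not those of the endpoint in SAP 3.2 and Protocol 10.4.1. Because OR is tabulated by regimen and dose level, in cohorts of a few patients, differences in case mix could also alter the apparent pattern across doses.

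**Working it through.** The documents state no response rate, and SAP 4.13 says no formal sample size calculation was done, so there is no planned figure to reproduce. The check has two parts: what the text leads to, and how much it could matter.

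**1. Following the text**

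- SAP 3.2.1.1 bases OR on BOR. BOR includes non-target-only patients: their time-point responses come from Table 2, and Non-CR/Non-PD is counted as SD.
- SAP 4.2 uses as denominator the number of patients providing data. A non-target-only patient with a BOR provides data and so stays in n.
- Table 2 allows CR, Non-CR/Non-PD, PD or NE. There is no PR row, but CR is possible.
- For change in sum of diameters, SAP 3.2.1.1 does limit the derivation to patients with target lesions. The OR derivation has no such limit.
- SAP 4.14 lists changes from the protocol's planned analyses. Dropping the measurable-disease restriction on OR is not among them.

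**2. Possible size**

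Let N be the FAS size, k the number without measurable disease, r the responders with measurable disease, and c the CRs among the k.

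- FAS rate = (r + c)/N
- Defined rate = r/(N − k)
- With c = 0: FAS rate = defined rate × (N − k)/N

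Inputs: N = 34 is the approximate planned Part 1 size (Protocol 10.1), used for illustration. r, k and c are not in the documents and are assumed. Intervals are two-sided exact 95% Clopper-Pearson, the SAP's own method.

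| k | Ratio (34 − k)/34 | Defined rate, r = 3 (95% CI) | Upper limit, r = 0 |
|---|---|---|---|
| 0 | 1.00 | 3/34 = 8.8% (1.9-23.7) | 10.3% |
| 3 | 31/34 = 0.91 | 3/31 = 9.7% (2.0-25.8) | 11.2% |
| 5 | 29/34 = 0.85 | 3/29 = 10.3% (2.2-27.4) | 11.9% |
| 10 | 24/34 = 0.71 | 3/24 = 12.5% (2.7-32.4) | 14.2% |

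With c = 0 the FAS result is the k = 0 row whatever k is. With r = 0 and c = 0 the rate is 0% either way and only the upper limit moves.

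At dose level, one responder and one non-measurable patient change 1/6 = 16.7% (0.4-64.1) to 1/5 = 20.0% (0.5-71.6), and 1/3 = 33.3% (0.8-90.6) to 1/2 = 50.0% (1.3-98.7).

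**Direction.** The FAS rate is a weighted average of r/(N − k) and c/k, so it exceeds the defined rate when c/k is the larger. With r = 3 and c = 1, the FAS rate is 4/34 = 11.8% (3.3-27.5). That is above 9.7% (k = 3) and 10.3% (k = 5), but below 12.5% (k = 10).

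**The case against.** The strongest reply is that the passages can be read together. An endpoint-level restriction can sit inside an analysis set, and Protocol 10.4.1 puts the FAS rule and the measurable-disease restriction in one section. The SAP also applies an FAS label to outputs that can contain only measurable-disease patients: Tables 14.2.4.3 and 14.2.4.4 and the waterfall plots of target-lesion change. The label on Table 14.2.4.1 therefore does not prove that OR is divided by the whole FAS. This stands as far as it goes: no sentence explicitly sets the OR denominator to all FAS patients. It does not remove the gap. For change in diameters the subset is written into the derivation. For OR it is not, and the BOR on which OR rests deliberately keeps non-target-only patients.

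A reader might also infer that the reported rate must be biased downward. The documents do not support that, since Table 2 permits a CR in a non-target-only patient and SAP 3.2.1.1 would count it as a response.

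Finally, little depends on the result. OR is a secondary endpoint in Part 1, analyses are descriptive (SAP 4.10.1.2), and RP2D selection rests on safety, PK and target engagement (SAP 3.1). Starred patient-level listings of lesions and responses would allow a recount. All of this stands, and it limits the importance of the point.

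**Conclusion.** The point holds as an inconsistency between the endpoint definition and the analysis instructions. Followed as written, the SAP can yield an OR rate and exact CI that are not those of the defined endpoint. Non-measurable patients lower the rate unless one reaches CR; a CR adds a responder from outside the defined population and may raise the rate.

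The size cannot be determined. With 3 measurable-disease responders among 34 patients, no CR in a non-target-only patient, and 3 to 10 non-measurable patients, the reported 8.8% compares with 9.7% to 12.5% for the defined endpoint, and the intervals overlap heavily. With no non-measurable patients the two agree exactly. The 34 is itself only a planned figure: SAP section 1 says enrolment stopped during Part 1. It would be too strong to conclude that the trial's response rate is in fact understated. The primary DLT analysis is unaffected. The correction is worth making because Table 14.2.4.1 goes into the abbreviated CSR.

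**What to change.** In SAP 3.2.1.1 and 4.10.2.1, state that the OR rate and its Clopper-Pearson interval, confirmed and unconfirmed, take both numerator and denominator from FAS patients with at least one target lesion at baseline. Restricting the denominator alone would leave a non-target-only CR in the numerator. Print that n for each regimen and dose level in Table 14.2.4.1. Keep the all-FAS BOR distribution and, if wanted, an all-FAS OR row as a supplementary display.

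If the sponsor instead intends OR on all dosed patients, remove the restriction from SAP 3.2 and record the departure from Protocol 10.4.1 in SAP 4.14.

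The cost is a sentence in each of the two sections and a table row. Target-lesion data are already recorded at every imaging time point, so nothing new is collected. The downside of the restriction is slightly wider intervals.
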